All study participants receive medication treatment for OUD with OUD treatment monitoring by a nurse care manager or medical provider (treatment as usual, or TAU) continually throughout the 12 month study. Those randomized to the intervention group will additionally receive Mindful Awareness in Body-oriented Therapy (MABT). The MABT protocol calls for eight sessions to be delivered over a 12 week period between baseline and the 12 week post-intervention assessment. At six months, those in the MABT+TAU treatment group with continued substance use will be offered an additional six sessions of MABT between the six month and 9 month assessments. Follow-up for all participants will total 12 months from the participant’s first assessment point.

Sample Size and Population

330 male and female individuals who have been receiving MAT treatment for at least four

weeks will be recruited from three OUD clinical treatment sites. Each study arm will include 165 participants. Participants will be randomized within site, and stratified by sex and self-reported chronic pain; objectives and outcomes will not vary by strata.

We expect the clinical characteristics of study subjects to be similar to those enrolled in the SAMHSA Medication Assisted Treatment - Prescription Drug and Opioid Addiction (MAT-PDOA) project in Washington State. The patients at the two clinics have near equivalence in the numbers of men and women served, and age range (18 - 70 years old) with the majority (59%) under the age of 35. Most patients are white, low-income, have at most a high school education, and are on public insurance (Medicare or Medicaid), with substantial mental health and substance use co-morbidity. Approximately 25% are minorities.

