Rationale for MABT as an Adjunct to MAT of OUD. [name] research focuses on an intervention, Mindful Awareness in Body-oriented Therapy (MABT), designed to teach interoceptive awareness. Findings from this program of research (including prior R21DA024771 and ongoing R01DA033324) highlight the role of improving interoceptive awareness through MABT to reduce substance use and improve health outcomes. This research indicates that avoidance of body sensations (emotional or physical) is common among individuals in SUD treatment.[83-85] In addition, maintaining attention to one's body sensations often exceeds these individuals' perceived capacities. [name] SUD research to date has focused on MABT as an adjunct to abstinence-based treatment for individuals using various primary substances (i.e., alcohol, amphetamines, opioids, etc.). Thus the proposed study patient characteristics and MAT program/setting are distinctly different from the sample and program/setting in prior MABT SUD studies (NIDA-funded R21 and R01). While psychiatric comorbidity is expected to be similar among past MABT study samples and the proposed study sample, co-morbid chronic pain is expected to be highly prevalent which it was not in prior SUD MABT studies. Likewise, the setting/treatment programs are distinctly different, involving regular visits to a medical setting for medication-assisted treatment but without the group psychoeducational program that defines intensive outpatient abstinence-based treatment. Also, while the results from a pilot study of Mindful Awareness in Body-oriented Therapy (MABT) for veterans with PTSD and comorbid chronic pain,[86] demonstrated the acceptability of MABT for chronic pain patients and the perceived positive impact on pain management, the study was not sufficiently powered to see changes on health outcomes. This proposal thus represents a next step in [name] research program to examine MABT specifically for individuals in office-based medication-assisted treatment for OUD, aligning with Stage II research to study for

whom and in what contexts this intervention may be beneficial;[87] this would be the first MABT SUD study to include men and the first MABT study sufficiently powered to examine the effect of MABT on individuals with comorbid chronic pain.

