MABT Reduces Psychological Symptoms and Improves Emotional Well-being, Mindfulness, and Interoceptive Skills: MABT SUD treatment research (R21 study) showed promising results with significant between-group differences with moderate to large effects on mental health outcomes between MABT+TAU compared to TAU at 9 months. These included depression symptoms, eating disorder symptoms, perceived stress, dissociation, and physical symptom frequency.[85] The R01 pre-post findings (N = 187) showed significant improvements for MABT compared to TAU in craving, depression among those that received the full intervention dose, improved emotion regulation (self-report and psychophysiology), interoceptive awareness, and mindfulness skills among the MABT completers.[89]. Longitudinal outcomes showed maintained improvements for MABT vs. TAU on craving, psychophysiology (well-being/regulation), interoceptive awareness and mindfulness skills.[90] The proposed study examines many of the same mental health and process variables as in the above studies.

Patients on MAT frequently suffer from chronic pain, which is a risk factor for opiate craving

and potential relapse. We conducted a cross-sectional study (K23DA027367) of 106 adults who were maintained on buprenorphine or methadone.[91] The primary outcome was cold pain tolerance assessed by cold-pressor test. Chronic pain was highly prevalent (67%), and current pain was even moreso (83%). These results reinforced that pain and hyperalgesia are common problems in this population of persons who were maintained on MAT for treatment of OUD. In a subsequent study performing secondary analysis on data from the same sample, we examined relationships between pain and opioid craving and opioid use as measured by urine drug testing (UDT).[92] We found that 51% reported craving opioids in the past week, and 16% had a positive UDT for opiates. We concluded that chronic pain with associated opioid craving potentially places this population at risk for relapse. Results from these two studies underscore that there is an unmet need for interventions to address pain among persons on MAT in order to prevent relapse and improve addiction treatment outcomes.

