Physical symptoms will be assessed using the Medical Symptoms Checklist (MSC) and pain severity and interference using the Brief Pain Inventory (BPI). The MSC measures the frequency (0-8 scale) and severity (0-10 scale) of 29 common physical symptoms.[19] The BPI is a validated, widely used measurement tool for assessing clinical pain. In the U.S. it has been validated in non-cancer patients with pain[18] and HIV-infected patients.[100] The assessment includes 13 questions which provide information on pain severity and pain interference in the past week. Participants are initially asked if they have experienced any significant pain in the past week, and if they respond positively they answer subsequent

questions about duration of pain, pain severity and interference. Pain severity is rated from 0 (“no pain”) to 10 (“worst pain imaginable”), and participants are asked to rate their current pain as well as pain at its worst, at its best, and on average in the past week. Pain interference includes information on the impact of pain on general activity, walking, work, mood, enjoyment of life, relations with others, and sleep, asking the participant to rate interference on a scale from 0 (“does not interfere”) to 10 (“completely interferes”), and is reported as the mean of seven questions. Participants who responded that they had no pain in the past week will be coded “0” for pain severity and interference. The BPI will be supplemented with a single question on duration of currently reported pain in order to establish whether the pain is acute or chronic.

Opioid craving will be assessed using a single item numeric scale.[5] Participants are asked: “On a scale of 0-10, please indicate how much craving you have experienced during the past week,” with responses anchored at “0=no craving at all” and “10-strongest craving ever”. Retention will be defined as days retained in the program, or time to program discharge. Program discharges are documented in the electronic medical record (EMR) and date of discharge will be extracted from the record.

R01-Specific Objective 3 Outcomes: Exploration of the effectiveness of additional MABT dose offered at 6 months to those with continued substance use compared to those with continued substance use at 6 months in the TAU will be assessed using the Time-Line Follow-Back Interview (TLFB)[3, 4] self-reported substance use as described in in the primary objective.

For description of the intervention, see Section 2.2.

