Following baseline data collection, participants will be randomized to treatment group by the Research Coordinator. Randomization will be provided by the project statistician. Stratified randomization by study site, baseline self-reported chronic pain, and gender, will be used to distribute participants evenly between the two treatment conditions at each facility and within each gender and experience of chronic pain. Randomization will use a modified minimization method algorithm[96] based on an overall imbalance score which measures how far out of balance (within strata) the study is for a given set of random assignments to ensure approximately equal accrual into the two experimental arms and to facilitate concealment of treatment assignments. After randomization (for those assigned to treatment group), the RC will contact the site interventionist to inform them of their new assigned participant to schedule the first intervention visit.

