9.2 Sample Size and Randomization

Sample Size Calculation/Power Analysis:

Primary Objective The power for the primary aim of this study was determined for change in the days percent abstinent from opioids on the Timeline Followback Interview (TLFB) between the study's two arms (MABT +TAU, and TAU only) from baseline to 6 months (R33 aim) and baseline to 12 months (R01 aim). The power analysis was based on the prior MABT SUD R01 study (N=187), in which the proportion of abstinent days for MABT + TAU was 88.6 compared to 80.0 for TAU at 12 month follow-up.[90] Unlike the count data used to assess the number of days abstinent, proportional data is based on exact binomial confidence intervals and thus provides reliable and appropriate data to use for sample size calculation. The magnitude of effect in this prior R01 is expected to be similar for baseline to 6 month (R33) and baseline to 12-month effect for MABT + TAU vs. TAU (R01) in the current study.

A sample of 330, with an expected loss to follow-up of 20%, allows for .80 power to detect a minimum difference in proportion in days abstinent between MABT and TAU of .14, alpha =.05, two-tailed. Loss to follow-up is not expected to vary significantly due to treatment assignment. Since the actual analyses allow GEE models to analyze five time points (0, 3, 6, 9, 12 months) simultaneously for the R01 study, power will very likely be higher than these conservative estimates.

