9.6 Data Analyses

Primary Analysis To test the primary hypotheses, generalized linear regression models for dependent data will be used to compare percent days abstinent from opioid use in the two study groups between baseline to 6 months for the R33 study aims, and baseline to 12 months for the R01 study aims. Sensitivity analyses will also explore modeling opioid use as percent days abstinent during the assessment periods using Generalized Estimating Equations (GEE) [106] with a logit link and an exchangeable correlation structure. We will fit difference within group correlations structures (unstructured, independent, exchangeable, autoregressive) seeking the correlation structure that combines the fewest parameters with the best measure of fit using Akaike information criterion (AIC) and Bayesian information criterion (BIC). The logarithm of the total number of days in the assessment period will be included as an offset variable to account for the time at risk of relapse. The same analysis will be done to examine percent days abstinent on other illicit drugs and alcohol.

Secondary Analyses Analyses of secondary outcomes (mental and physical health outcomes and opioid craving) will utilize GEE as described above. Longitudinal analyses will examine treatment by time interactions on each of the outcomes. Analyses of retention in medication-assisted treatment will be done using a test of proportions retained in MAT as well as the log-rank test to compare survival curves. A sensitivity analysis will use Cox regression to adjust for pre-treatment covariates. Last, we plan to include exploratory analyses to also examine treatment by gender interactions.

Exploratory Analysis Linear regression model using GEE will be used to explore the effect of additional MABT dose on days abstinent from opioid use and related health outcomes at 12 months among the MABT 6 month non-responders compared to control non-responders. Characteristics of responders will be compared to those of non-responders using t-tests, chi-square, or Fisher's exact tests.

In addition, we will explore the relationship with dose, within the MABT group. Dose response functions will be estimated thorough a regression approach treating the number of sessions as the continuous treatment variable. Such models are appropriate when the treatment intensity is endogenous (that is, selection into treatment depends on both observable and unobservable factors).

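### Section 2.1 claims adequate power in people with comorbid chronic pain, a randomisation stratum, but no planned analysis, population or power figure addresses that group

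*Combined protocol and SAP*

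**What the plan says.** The last part of section 2.1 distinguishes this trial from an earlier MABT pilot in veterans with chronic pain, which it describes as too small to show changes in health outcomes. It calls the present trial "the first MABT study sufficiently powered to examine the effect of MABT on individuals with comorbid chronic pain".

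Chronic pain is built into the allocation. Section 6.2.2 states: "Stratified randomization by study site, baseline self-reported chronic pain, and gender, will be used"; sections 3, 4.3 and 9.2 agree. No inclusion criterion in 4.1 requires pain, so people with and without chronic pain are enrolled.

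The Précis (Sample Size and Population) says participants are "stratified by sex and self-reported chronic pain; objectives and outcomes will not vary by strata". Section 9.2 gives one whole-sample statement for secondary outcomes, 80% power for 0.4 SD. Section 9.3 defines an intent-to-treat population, a dose population and a subpopulation of six-month users, but none for chronic pain. Section 9.6 analyses secondary outcomes by GEE with treatment-by-time interactions and adds: "Last, we plan to include exploratory analyses to also examine treatment by gender interactions". It names no chronic-pain subset, no stratum term and no treatment-by-pain interaction.

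On the BPI (sections 3, 9.1 and 9.5.2): "Participants who responded that they had no pain in the past week will be coded" as 0 for severity and interference.

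**The concern.** The protocol gives a reason for doing the trial (learning what MABT does for people with chronic pain) and balances the arms on that factor, but the statistical sections never return to it. Following the plan as written yields one BPI contrast over everybody. That contrast answers whether MABT lowers average pain across the clinic population, not what it does for someone with chronic pain. Any chronic-pain estimate produced later would be an unplanned subgroup result, although the stratum is fixed at baseline and balanced by design. The power claim in 2.1 would be carried forward with no calculation behind it.

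**Working it through.** **Inputs.** 330 randomised 1:1 with 20% loss, hence 132 per arm (9.2). Test level "alpha =.05, two-tailed" is stated for the primary outcome and assumed here for secondary ones. The documents give no chronic-pain prevalence for this trial. Section 2.2 reports 67% chronic and 83% current pain in the team's cross-sectional sample of 106 adults on buprenorphine or methadone. I assume 67%, with a range of 50% to 83%.

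**Formulas** (two-sample normal approximation, outcome in SD units, n per arm): power = Φ(d·√(n/2) − 1.96); difference detectable at 80% power = (1.96 + 0.84)·√(2/n).

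**The plan's own figure.** With n = 132 and d = 0.4: 0.4 × √66 = 3.25, and Φ(1.29) = .90. The difference detectable at 80% power is 0.345 SD. The stated 80% at 0.4 SD does not reproduce, but it errs on the cautious side. It needs 99 per arm, against 132 expected.

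**The chronic-pain stratum:**

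| Assumed prevalence | n per arm | Power at 0.4 SD | Detectable at 80% |
|---|---|---|---|
| 50% | 66 | .63 | 0.49 SD |
| 67% | 88 | .76 | 0.42 SD |
| 75% | 99 | .80 | 0.40 SD |
| 83% | 110 | .84 | 0.38 SD |

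For the 67% row: 132 × .67 = 88.4; 0.4 × √44.2 = 2.66; Φ(0.70) = .76; 2.80 × √(2/88.4) = 0.42.

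**Treatment-by-chronic-pain interaction at 67%.** SE = √(2/88.4 + 2/43.6) = 0.262 SD. The detectable difference in effects is 2.80 × 0.262 = 0.73 SD. Power for a 0.4 SD difference is Φ(0.4/0.262 − 1.96) = Φ(−0.43) = .33.

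**What the whole-sample estimate averages.** If the effect is 0.4 SD with chronic pain and nil without it (an assumption), the whole-sample effect is .67 × 0.4 = 0.27 SD, one third smaller. At 50% it is 0.20 and at 83% it is 0.33. For the whole sample to show 0.4 SD, the chronic-pain effect would have to be 0.4/.67 = 0.60 SD.

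**Does the whole sample also lose power?** Let p be the prevalence and N = 132, and suppose people outside the stratum are constant at 0.

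- *Stratum-adjusted.* The effect is p·d and the residual SD is √p, so the standardised signal is (p·d/√p)·√(N/2) = d·√(pN/2). That is exactly the stratum's own value: power .76 either way.
- *Change from baseline.* Assume a baseline-to-follow-up correlation of .5, so the SD of change in the pain group is 1. The variance is .67 in the control arm and .67 + .67 × .33 × 0.4² = .705 in the MABT arm. SE = √((.67 + .705)/132) = 0.102. Power = Φ(0.268/0.102 − 1.96) = .75.
- *Follow-up scores only, nothing adjusted.* If the pain group's mean is 1.5 to 3 times its SD (assumed), the mixture SD is √(.67 + .2211 × mean²) = 1.08 to 1.63, and power falls to .52 to .27.

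Only the third case shows a material loss. Section 9.2 describes GEE over five time points including baseline, and 9.6 examines treatment by time, so the natural reading of the plan is close to the second case.

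**The case against.** The best defence is that pain was always a whole-sample question. The hypotheses in 1.2 and 9.1 concern pain in all participants, the Précis says objectives do not vary by strata, and 4.3 gives balance as the purpose of stratifying. On that view the intent-to-treat contrast is the right estimand and 2.1 is loose background prose. The stratum is also not badly powered: .76 at 67% prevalence and .80 at 75%.

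Most of this stands. It supports keeping the whole sample as lead analysis, and it makes the power claim unsupported rather than false. It does not reconcile 2.1 with the Précis, and it supplies no analysis for the group that 2.1 names.

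A reader might go further and infer that the whole-sample analysis is much weaker than a stratum analysis because pain-free people add noise. The documents do not support this. A figure such as .59 (0.27 SD with the SD left at 1) gives people who are constant at 0 the same spread as people in pain. With their variance at zero, the stratum-adjusted power is .76, and a baseline-inclusive model removes most of the gap between strata.

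Nor are the zero-coded people the non-chronic stratum. The coding follows past-week pain at each visit, not baseline chronic pain. With 83% current and 67% chronic pain, and if everyone with chronic pain also has current pain, about half of the non-chronic group (16 of 33 points) has pain that could improve. If the whole 83% responded equally at 0.4 SD, whole-sample power would be .77 with SD unchanged, no worse than the stratum. Coding 0 is also proper when someone's pain has resolved.

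**Conclusion.** The point holds as a gap between a stated purpose and the analysis plan. Section 2.1 makes a power claim for people with chronic pain; 9.2, 9.3 and 9.6 contain nothing that could support it. The consequence for interpretation is an averaged estimate, about one third smaller than the chronic-pain effect at 67% prevalence. That size rests on two assumptions: the prevalence, borrowed from a 106-person sample, and no effect outside the stratum.

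Two stronger conclusions do not follow. The claim in 2.1 is not shown to be wrong, since 80% power at 0.4 SD would be reached at about 75% prevalence. And nothing shows that the subgroup should replace the intent-to-treat sample as lead population for the BPI; that would trade away the objective as written without an established gain in power. Pain is a secondary outcome, and the primary test is untouched.

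**What to change.** Keep the intent-to-treat whole sample as the lead analysis for BPI severity and interference. Then, before any outcome data are seen by group:

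1. In 9.6, include the randomisation strata (site, gender and baseline chronic pain) in the models.
2. In 9.3 and 9.6, prespecify the treatment effect with confidence interval on BPI severity and interference within the baseline chronic-pain stratum, as recorded at randomisation.
3. In 9.6, add an exploratory treatment-by-chronic-pain interaction beside the gender one, labelled low-powered (about .33 for a 0.4 SD difference in effects at 67% prevalence).
4. In 2.1, replace the power claim with the detectable effect and its assumptions: about 0.42 SD at 80% power (power .76 at 0.4 SD) if 67% have chronic pain and 20% are lost, range 0.38 to 0.49 SD for prevalences of 83% down to 50%. Reconcile the Précis sentence on strata with this.

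The cost is wording and a few model terms on data already being collected, with no new visits or participants. The downsides are one more low-powered exploratory test and a slightly less favourable power statement.

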2.2 Study Rationale

Mindful Awareness in Body-oriented Therapy as an Adjunct to SUD Treatment. Prior NIDA-funded studies of MABT for SUD treatment provide an empirical basis for the design and methods of the current proposal. The results of prior study (R21) comparing MABT+TAU to TAU only (N = 46) and results from recently completed study (R01) of MABT comparing MABT+TAU to TAU only and Women’s Health Education (to control for time and attention) (N = 217) in women’s SUD treatment are summarized below. Both studies used the manualized MABT protocol, to be implemented in the proposed study. [name] experience developing, implementing, and disseminating results of previous MABT studies provide a logical and tested background for this research.

MABT Implementation as an Adjunct to Community - Based SUD Treatment: MABT implementation as an adjunct to SUD treatment is highly acceptable to patients and staff at community treatment facilities.[88] [name] R01 was implemented in three community SUD clinics in the Seattle area, the vast majority of participants are very low SES (85% unemployed, 87% on Medicaid or Medicare, and 43% highest level of education was high school), similar to the characteristics we expect in the proposed sample.[89]. Likewise, comorbid mental health distress in the R01[89] and prior R21,[85] particularly PTSD (68%) and depression (34% with moderate - severe symptoms), is comparable to what is expected in the proposed study sample (see Section 4).

MABT Reduces Substance Use Outcomes: MABT SUD treatment research (R21 study) showed significant reduction in substance use for MABT+TAU as measured by the percent days abstinent (primary outcome) on the Time Line Follow-Back Interview (TLFB) compared to TAU only.[85] R01 findings (N =187) show significant reductions in the percent days abstinent (also using the TLFB as primary outcome) in MABT+TAU compared to TAU only at 6 month and 12 month follow-up.[90]

MABT Reduces Psychological Symptoms and Improves Emotional Well-being, Mindfulness, and Interoceptive Skills: MABT SUD treatment research (R21 study) showed promising results with significant between-group differences with moderate to large effects on mental health outcomes between MABT+TAU compared to TAU at 9 months. These included depression symptoms, eating disorder symptoms, perceived stress, dissociation, and physical symptom frequency.[85] The R01 pre-post findings (N = 187) showed significant improvements for MABT compared to TAU in craving, depression among those that received the full intervention dose, improved emotion regulation (self-report and psychophysiology), interoceptive awareness, and mindfulness skills among the MABT completers.[89]. Longitudinal outcomes showed maintained improvements for MABT vs. TAU on craving, psychophysiology (well-being/regulation), interoceptive awareness and mindfulness skills.[90] The proposed study examines many of the same mental health and process variables as in the above studies.

Patients on MAT frequently suffer from chronic pain, which is a risk factor for opiate craving

and potential relapse. We conducted a cross-sectional study (K23DA027367) of 106 adults who were maintained on buprenorphine or methadone.[91] The primary outcome was cold pain tolerance assessed by cold-pressor test. Chronic pain was highly prevalent (67%), and current pain was even moreso (83%). These results reinforced that pain and hyperalgesia are common problems in this population of persons who were maintained on MAT for treatment of OUD. In a subsequent study performing secondary analysis on data from the same sample, we examined relationships between pain and opioid craving and opioid use as measured by urine drug testing (UDT).[92] We found that 51% reported craving opioids in the past week, and 16% had a positive UDT for opiates. We concluded that chronic pain with associated opioid craving potentially places this population at risk for relapse. Results from these two studies underscore that there is an unmet need for interventions to address pain among persons on MAT in order to prevent relapse and improve addiction treatment outcomes.

In summary, these preliminary studies demonstrate that MABT reduces substance use and comorbid mental health distress among women in abstinence-based SUD outpatient treatment, suggest that the MABT intervention can restore interoceptive function in the face of SUD, and point to the importance of addressing chronic pain in MAT for OUD. However, MABT has not yet been examined as an adjunct to MAT with an exclusively OUD sample nor have MABT studies included targeted pain outcomes, crucial to address the need for nonpharmacological supports for MAT treatment during this opioid epidemic. Furthermore, MABT has not been studied in a more generalized sample of women and men. This study is designed to accomplish these critical next steps.

Mindful Awareness in Body-Oriented Therapy. The MABT protocol and training manual teaches interoceptive awareness and self-care skills for emotion regulation to facilitate improved health outcomes (see Explanatory Model, Figure 1 below).

Figure 1. MABT Explanatory Model

Content	Key Processes	Outcomes
Body Literacy	↑ Interoceptive Awareness and Mindfulness Skills	↓ Substance Use and Craving
Interoceptive Training		↓ Mental Health Distress/Symptoms
Mindful Body Awareness	↑ Interoceptive Skills for Self-Care Integrated into Daily Life	↑ Emotional Well-being
		↓ Pain Severity and Interference

MABT involves delivery of eight 75-minute one-on-one sessions, once per week. MABT is distinctive in its explicit focus on the development of interoceptive awareness skills for emotion regulation. Strategies for addressing interoceptive dysfunction are not well developed in typical group mindfulness-based approaches of individual psychoeducational approaches that include a somatic focus. To address this issue, MABT provides an individualized protocol for scaffolding interoceptive awareness in the face of baseline

difficulty in attending to interoceptive signals, through a combination of psychoeducational and somatic approaches explicitly addressing difficulties with interoceptive processing. Used in multiple clinical trials, [83, 85, 86, 93-95] the protocol has an incremental approach for teaching interoceptive awareness to facilitate development of interoceptive awareness skills (see Table 2).

Table 2. Key MABT Elements (*number of minutes each session*)

Stage 1 (Sessions 1- 2)	Stage 2 (sessions 3-4)	Stage 3 (sessions 5-8)
Check-in (20)	Check-in (20)	Check-in (20)
Massage/Body Literacy (40)	Massage/Body Literacy (10)	Massage/ Body Literacy (10)
	Interoceptive Training (30)	Mindful Body Awareness (30)
Session Review (15)	Session Review (15)	Session Review (15)
Homework	Homework	Homework

The MABT intervention is designed to increase self-awareness and thus participants sometimes experience discomfort, emotions, as well as insight. Overall MABT is very low risk, as the protocol is designed to be individualized to ensure safety and comfort of the participant. To date, here have been no serious adverse events associated with any MABT study.

For participants initially assigned to MABT who report continued use of opiates or other substances at 6 months, an additional 6 MABT sessions will be offered.

